10.9. LUX-Dx ICM Not in Service, Disabled, or Explanted

If the LUX-Dx ICM is permanently programmed off and not in service per investigator's decision, disabled due to device issue or malfunction, or explanted for any reason following a successful implant, the reasons for such actions must be recorded on the appropriate CRFs. Subjects with the LUX-Dx ICM disabled, but still implanted will be withdrawn from the study. If disabling of the ICM is a result of an adverse event, these subjects must be followed at least 30 days to assure any associated adverse events are followed to resolution or closure of the event with ongoing or chronic status before withdrawal. The safety check attempts must be made between 30 days and 60 days after the ICM is permanently programmed off or disabled. The withdrawal must occur after the resolution of all reportable adverse events and the completion of the safety check.

All subjects undergoing explant must be followed at least 30 days post explant to ensure any associated adverse events, related to explant or otherwise, are followed to resolution, or closure of the event with ongoing or chronic status. The safety check attempts must be made between 30 days and 60 days after the explant procedure. These subjects must be withdrawn from the study after satisfying the follow-up period of at least 30 days for the safety check.

Print any applicable TSF for this visit. Data and source documentation requirements are summarized below in Table 10-7.

Data Collection	Retention of Original Source Documentation
Not in service, disabling, and explant information	Study site
Reportable adverse events (as defined in Section 19.1) and protocol deviations, if applicable	Study Site

Table 10-7: Device Not in Service, Disabling, and Explant Source Documentation

10.10. End of Study

The End of Study CRF must be completed following completion of the subject's 12-month $(\pm 30 \text{ days})$ EMR review, upon withdrawal of subject from the study, or upon subject's death. The subject's final status, including confirmation of a successful LATITUDE Clarity device transmission within the last 90 days, will be recorded on the End of Study CRF. There is no in-office visit requirement for this study procedure.

If a subject is experiencing a reportable adverse event at the time of study completion, the study site shall continue following the subject through resolution of the adverse event or closure of the adverse event as chronic or ongoing prior to completing the End of Study CRF.

Upon completion of the study, the subjects will be followed according to the site's standard of care.

10.11. Source Documents

It is preferable that original source documents are maintained, when available. In lieu of original source documents, certified copies are required to be maintained. A certified copy is

	Form/Template 92120219_Rev/Ver D
Confidential	LUX-Dx PERFORM Protocol, 92557593, Rev/Ver C
	Page 36 of 66
a copy (irrespective of the type of	of media used) of the original record that has been verified
(i.e., by a dated signature or by g	generation through a validated process) to have the same

information, including data that describe the context, content, and structure, as the original.

11. Statistical Considerations

11.1. Objectives

11.1.1. Primary Effectiveness Objective 1

The primary effectiveness objective 1 is to characterize the utilization of the remote programming feature.

11.1.1.1.Hypotheses

There is no formal hypothesis as this objective is exploratory.

11.1.1.2. Sample Size

There is no formal hypothesis for primary effectiveness objective 1 and no formal sample size requirements for this objective. The overall sample size is driven by the primary effectiveness objective 2 and primary safety endpoint – acute. See section 11.1.5 for more details.

11.1.2. Primary Effectiveness Objective 2

The primary effectiveness objective 2 is to characterize the performance of arrhythmia detection algorithm.

11.1.2.1.Hypotheses

There is no formal hypothesis as this objective is exploratory.

11.1.2.2. Sample Size

11.1.3. Primary Safety Endpoint - Acute

The primary safety endpoint – acute is LUX-Dx ICM system-related complication-free rate at 30 days post-implant. The ICM system refers to the LUX-Dx ICM device, mobile apps, and the associated accessories used with the device. See section 11.1.5 for more details.

11.1.3.1.Hypotheses

The primary safety endpoint - acute hypotheses are:

- H₀: ICM system-related complication-free rate at 30 days post-implant $\leq 94\%$
- HA: ICM system-related complication-free rate at 30 days post-implant > 94%

11.1.3.2. Statistical Methods

The ICM system-related complication-free rate at 30 days post-implant will be calculated using Kaplan-Meier methodology. The 97.5% one-side lower pointwise confidence limit of

	Form/Template 92120219_Rev/Ver D
Confidential	LUX-Dx PERFORM Protocol, 92557593, Rev/Ver C
	Page 38 of 66

the ICM system-related complication-free rate will be calculated via log-log methodology and compared to the performance target of 94%. If the lower confidence limit exceeds 94% then the null hypothesis will be rejected.

The adjudication of the ICM system-related adverse events and complications will be conducted by independent physician reviewer(s).

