9.1. Point of Enrollment

Subjects will be considered enrolled into the study at the time of study-specific ICF execution. All subject enrollments will be counted against the enrollment ceiling for the study.

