9.5. Subject Status and Classification

Enrolled subjects will be classified as follows:

Intent refers to a subject who has been enrolled in the study but then does not have local anesthetic administered in preparation for a LUX-Dx ICM implant procedure. The original ICF and enrollment documentation for intent subjects should be maintained in the study file. The Intent subjects must be withdrawn from the study and the End of Study CRF completed. If the Intent subject is withdrawn due to reason of eligibility violation, a protocol deviation is required. There are no follow-up requirements for intent subjects.

Attempt refers to a subject who has been enrolled in the study, has had local anesthetic administered in preparation for the implant procedure of a LUX-Dx ICM, but is not successfully implanted with the LUX-Dx ICM. Attempt subjects must be followed at least 30 days post implant attempt and all reportable adverse events associated with the LUX-Dx ICM or attempted implant procedure must be reported and followed to resolution, or closure of the event with ongoing or chronic status. The safety check attempts must be made between 30 days and 60 days after the attempted implant procedure. These subjects must be withdrawn from the study and the End of Study CRF completed after the resolution of all reportable adverse events and the completion of the safety check.

Implant refers to a subject who has been enrolled in the study and is successfully implanted with the LUX-Dx ICM. These subjects are followed in accordance with the protocol and included in all applicable analyses.

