Data Collection	Retention of Original Source Documentation
Information regarding the extended Holter monitor distribution, return, and data download and transmission	Study Site
Downloaded Holter monitor device raw data	Core lab and BSC
Extended Holter monitoring report and ECG strips	Core lab; a report copy is sent to BSC and Study Site
Reportable adverse events (as defined in Section 19.1) and protocol deviations, if applicable	Study Site

Table 10-5: 2-Month Holter Visit Source Documentation

10.8. 6-Month and 12-Month EMR Review (±30 days)

A review of each implanted subject's EMR must be performed at 6 months (\pm 30 days) and 12 months (\pm 30 days) post-ICM implant. Subjects are not required to visit the study site in-person. Reportable adverse events defined in Section 19.1 shall be collected. To supplement the EMR review, a phone call or virtual health visit to the subject must be attempted and documented to obtain adverse event information that may not be recorded in the EMR. If the subject is seen in-office that might be part of the standard-of care, then a phone call/virtual health visit is not required. It is not a study deviation if the subject cannot be reached by phone or virtual health visit despite attempts. In addition, any ICM reprogramming (to be documented throughout the study duration), arrhythmia diagnoses facilitated by the ICM, and the resulting arrhythmia treatments will be collected on the appropriate CRF. Site staff will confirm successful LATITUDE Clarity device transmission within the last 90 days to determine if the subject may be considered lost to follow-up.

Site is encouraged to perform the EMR review at the time of an in-office standard of care visit, if possible.

Print a copy of initial LATITUDE Clarity programming report to verify the time of the latest device transmission and print the applicable TSF for this visit. Data and source documentation requirements are summarized below in Table 10-6.

Data Collection	Retention of Original Source Documentation
ICM device transmission information	Study site
Information on arrhythmia diagnoses and related treatments since the LUXDx ICM implant	Study site
Reportable adverse events (as defined in Section 19.1) and protocol deviations, if applicable	Study Site

Table 10_6. 6.	and 12-Month	FMR Review	Source Documentation
1 abic 10-0. 0.	· and 12-month	THIN VENICA	Source Documentation

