11.1.4.2. Statistical Methods

The ICM system-related complication-free rate at 12 months post-implant will be calculated using Kaplan-Meier methodology. The 97.5% one-side lower pointwise confidence limit of the ICM system-related complication-free rate will be calculated via log-log methodology and compared to the performance target of 93%. If the lower confidence limit exceeds 93% then the null hypothesis will be rejected.

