11.1.5. Overall Sample Size

Approximately 600 to 827 subjects will be enrolled to fulfill the objectives and safety endpoints. Approximately 600 subjects are desired for sufficient data in the Holter study for primary effectiveness objective 2, and 227 subjects are needed for the safety endpoints. A total of 227 enrollments are required for the safety endpoint, but the first 227 subjects are not required to enroll in the extended Holter study. Thus, if the first 227 subjects enroll in the Holter study then the minimum sample size would be 600. If none of the first 227 subjects enroll in the Holter then a maximum sample size would be 827.

Primary effectiveness objective 2 sample size details can be found in section 11.1.2.2, and safety endpoint sample size details can be found in section 11.1.3.3.

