11.2. General Statistical Methods

11.2.1. Analysis Sets

Data from Implant and Attempt subjects will be used for each objective and endpoint as appropriate. Further details will be outlined in the Statistical Analysis Plan.

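### Should the 30-day safety decision use an exact lower limit instead of the log-log limit, and does the plan need a written rule for zero events?

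*Combined protocol and SAP*

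**What the plan says.** Both safety decisions rest on a Kaplan-Meier estimate and a one-sided limit. For the 30-day endpoint section 11.1.3.2 reads "The 97.5% one-side lower pointwise confidence limit of" and continues "the ICM system-related complication-free rate will be calculated via log-log methodology and compared to the performance target of 94" per cent. For the 12-month endpoint (section 11.1.4.2) the limit "will be calculated via log-log methodology and compared to the performance target of 93" per cent. In each case the null hypothesis is rejected if the limit lies above the target.

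Section 7.3 gives 227 subjects for the acute endpoint and 226 for the chronic one. Section 11.1.5 counts the former as enrolments: "A total of 227 enrollments are required for the safety endpoint". Section 9.1 fixes enrolment at consent: "Subjects will be considered enrolled into the study at the time of study-specific ICF execution". Section 9.5 says of those who never reach local anaesthetic: "There are no follow-up requirements for intent subjects". Section 11.2.1 says: "Data from Implant and Attempt subjects will be used for each objective and endpoint as appropriate", and leaves further detail to a separate Statistical Analysis Plan, which is not in the text reviewed. The text of section 11.1.3.3, which holds the safety sample-size derivation, is not in it either.

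**The concern.** Two features of the log-log limit look unhelpful.

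First, the evaluable number will probably be below 227, because Intent subjects count as enrolled but contribute no follow-up. If 9 to 12 of the 227 drop out this way (9/227 = 4.0%, 12/227 = 5.3%), a result with 6 complications fails under log-log and passes under an exact limit. The verdict on the device would then turn on one event because of the interval formula alone.

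Second, with no complications the estimate is 1 and log(−log 1) is undefined. The visible text gives no rule for that case, so the written test cannot be evaluated for the best possible outcome. For a low-risk device that outcome is not remote.

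**Working it through.** **The plan's own figure.** 227 cannot be reproduced: the expected rate, the power and any attrition allowance are not in the text reviewed. That is not counted against the plan. True rates and losses below are assumptions.

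**Inputs.** One-sided 97.5% (z = 1.96); targets 94% and 93%; planned numbers 227 and 226.

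**Formulas, d events among n, no censoring before the time point.**
- Log-log: S = 1 − d/n; v = d/(n(n − d)); lower limit = S^exp(z√v/|ln S|).
- Exact (Clopper-Pearson): the 2.5% quantile of Beta(n − d, d + 1).

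**Worked case, n = 215, d = 6.** S = 0.97209, √v = 0.011555, |ln S| = 0.028304. The exponent is exp(1.96 × 0.011555/0.028304) = 2.226, and 0.97209^2.226 = 0.9389. The exact limit is 0.9403.

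**Six events, target 94%.**

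| n (lost) | Log-log | Exact | Decision |
|---|---|---|---|
| 227 (0) | 94.21% | 94.34% | both pass |
| 219 (8) | 94.004% | 94.13% | both pass |
| 218 (9) | 93.98% | 94.11% | exact only |
| 215 (12) | 93.89% | 94.03% | exact only |
| 214 (13) | 93.87% | 93.998% | both fail |

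At n = 227 seven events fail under both (93.64% and 93.75%). Over the 48 values from 180 to 227 the permitted event count differs at only 9: n = 192–196 (4 v 5) and n = 215–218 (5 v 6).

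**Error rate.** At n = 215 and a true 94%, the chance of passing is 0.97% under log-log and 2.42% under exact. Over n = 180 to 227 the log-log maximum is 2.09%. The planned rule is valid throughout.

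**Power at the worst point, n = 215 (log-log v exact).** True 97%: 37.3% v 53.3%. True 98%: 73.8% v 85.8%. True 99%: 97.8% v 99.4%. Each difference is the probability of exactly 6 events.

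**Average gain in percentage points, with evaluable n binomial from 227.**

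| True rate | 0% loss | 2% | 4% | 5% | 6% | 8% |
|---|---|---|---|---|---|---|
| 97.5% | 0 | 0.6 | 6.8 | 7.2 | 5.1 | 1.2 |
| 98% | 0 | 0.5 | 5.3 | 5.5 | 3.9 | 0.9 |
| 98.5% | 0 | 0.3 | 2.7 | 2.9 | 2.0 | 0.5 |
| 99% | 0 | 0.1 | 0.7 | 0.7 | 0.5 | 0.1 |

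The chance that n falls in 215–218 is 4% at 2% loss, 43% at 4%, 46% at 5% and 7% at 8%.

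**When the loss occurs.** The table of limits assumes that the lost subjects leave the risk set before the events, as Intent subjects do. If they are censored after the events, the log-log limit stays at 94.21% and 6 events pass.

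**Twelve months.** Clopper-Pearson does not handle censoring. The natural replacement, the beta-product limit, was simulated at n = 226 and a true 97.5%, with 12,000 datasets per scenario. Power, log-log v beta-product, at 2%, 5% and 10% dropout:
- everyone followed to day 365: 83.1 v 88.1, 81.2 v 83.2, 82.5 v 82.7;
- half censored between days 335 and 365, which the 30-day tolerance in section 10.8 permits: 81.9 v 65.5, 80.5 v 63.4, 80.5 v 58.0, a loss of 16.4, 17.1 and 22.5 points.

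**Zero events.** The probability at n = 227 is 0.98^227 = 1.0%, 0.99^227 = 10.2% and 0.995^227 = 32.1%. The exact limit is then 0.025^(1/227) = 98.4%, and the same to one decimal at 226. With 110 still at risk it is 0.025^(1/110) = 96.7%. It falls below 93% only with 50 or fewer at risk (0.025^(1/50) = 92.89%).

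**The case for a change.** The best argument for changing is that the acute switch costs only wording and a few lines of code, keeps the error below 2.5%, and never loses power when there is no censoring. It gains most at a loss of 4 to 5%, which is plausible when enrolment is counted at consent. The hidden derivation may even sit at that spot. An exact-binomial requirement of 215 (true rate 98%, power at least 80%) with 5% attrition gives 215/0.95 = 226.3, rounded up to 227. For the chronic endpoint, 203/0.90 = 225.6 gives 226. If those were the planned evaluable numbers, log-log would allow one event fewer at both (5 v 6, and 6 v 7).

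The arithmetic stands, but the inference does not go far. That derivation is back-solved and is not the only one that fits: with all 227 evaluable, power at 98% is 82.8% under either limit. Even if it were right, the cost is some power for the sponsor, not a false claim of safety. The acute switch would loosen a pass rule in a single-arm study where sponsor staff review safety data as they arrive (section 21.1), so a change after events have accrued could look data-driven. It would also leave the two endpoints with different primary limits, since the 12-month results argue for keeping log-log there.

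On zero events, it is true that a convention is better written beforehand. However, any sensible analyst would report an exact limit, and the separate analysis plan may already say so. Whether the 227 includes Intent subjects is likewise analysis-set detail that section 11.2.1 defers to that plan.

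**Conclusion.** No change is needed. The plan specifies a standard limit completely (level, scale, target and decision rule), and that limit errs in the direction that protects patients. The difference from an exact limit is one event, at 9 of the 48 sample sizes from 180 to 227, and none at full enrolment. The average power at stake peaks near 5.5 points at a true 98% and 5% loss, rises to about 7 points at 97.5%, and is 0.7 points or less at 99% and above. Those sizes rest on assumed true rates, assumed losses, and losses that precede the events. Against them stands a possible loss of 16 to 22 points at 12 months if the same family of limits were used there, or two primary methods if it were not. That is a fair trade-off already settled on the conservative side.

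The zero-event case is a gap that analysts fill sensibly. With about 227 at risk the exact limit is 98.4%, clear of both targets, so the conclusion would not be in doubt.

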11.1.4. Primary Safety Endpoint - Chronic

The primary safety endpoint – acute is LUX-Dx ICM system-related complication-free rate at 12 months post-implant.

11.1.4.1.Hypotheses

The primary safety endpoint - chronic hypotheses are:

- H₀: ICM system-related complication-free rate at 12 months post-implant $\leq 93\%$
- HA: ICM system-related complication-free rate at 12 months post-implant > 93%

11.1.4.2. Statistical Methods

The ICM system-related complication-free rate at 12 months post-implant will be calculated using Kaplan-Meier methodology. The 97.5% one-side lower pointwise confidence limit of the ICM system-related complication-free rate will be calculated via log-log methodology and compared to the performance target of 93%. If the lower confidence limit exceeds 93% then the null hypothesis will be rejected.

11.1.5. Overall Sample Size

Approximately 600 to 827 subjects will be enrolled to fulfill the objectives and safety endpoints. Approximately 600 subjects are desired for sufficient data in the Holter study for primary effectiveness objective 2, and 227 subjects are needed for the safety endpoints. A total of 227 enrollments are required for the safety endpoint, but the first 227 subjects are not required to enroll in the extended Holter study. Thus, if the first 227 subjects enroll in the Holter study then the minimum sample size would be 600. If none of the first 227 subjects enroll in the Holter then a maximum sample size would be 827.

Primary effectiveness objective 2 sample size details can be found in section 11.1.2.2, and safety endpoint sample size details can be found in section 11.1.3.3.

11.2. General Statistical Methods

11.2.1. Analysis Sets

Data from Implant and Attempt subjects will be used for each objective and endpoint as appropriate. Further details will be outlined in the Statistical Analysis Plan.

11.2.2. Control of Systematic Error/Bias

The number of subjects each center can enroll will be capped and poolability of data will be tested across centers to assess heterogeneity. Additionally, the first 227 enrollments for the safety cohort will not be required to enroll in Holter study to avoid subject selection bias.

Form/Template 92120219_Rev/Ver D Confidential LUX-Dx PERFORM Protocol, 92557593, Rev/Ver C Page 40 of 66

11.2.3. Number of Subjects per Investigative Site

To avoid any study site effect and bias, no single site will enroll more than 90 subjects of the total enrollments in the study and 34 subjects for the safety endpoint, without prior approval from BSC.

11.3. Data Analyses

11.3.1. Interim Analyses

There are no formal interim analyses. Interim analyses may be performed to support publications or regulatory product approval in geographies outside of US. The number of subjects required for the Holter study will be re-estimated during the study using an observed AF incidence rate and data loss rate to obtain approximately 100 subjects with a true AF episode.

11.3.2. Subgroup Analyses

Objectives may be performed in various subgroups including but not limited to:

- Reason for monitoring
- Sex (Male vs. Female)
- Age (< 65 years vs. \geq 65 years)
- BMI (Obese vs. Overweight vs. Normal)
- History of atrial arrhythmia (All types vs. None)
- Programming Parameters

Further details will be outlined in the Statistical Analysis Plan.

11.3.3. Justification of Pooling

The poolability of data by center will be assessed to determine if there is heterogeneity of data among the different centers. Further details of poolability testing will be outlined in the Statistical Analysis Plan.

11.3.4. Multivariable Analyses

Multivariable analyses will be detailed in the statistical analysis plan.

11.3.5. Changes to Planned Analyses

Any changes to the planned statistical analyses made prior to performing the analyses will be documented in an amended Statistical Analysis Plan approved prior to performing the analyses. Changes from the planned statistical methods after performing the analyses will be documented in the clinical study report along with a reason for the deviation.

12. Health Economics Outcomes

A formal health economics analysis may be completed as part of the LUX-Dx PERFORM Study. This will take into consideration any differences in complication rates and resource utilization. These inputs may be used in health economics analyses performed.

13. Data Management

13.1. Data Collection, Processing, and Review

Subject data collected on the Case Report Form (CRF) will be recorded in a limited access secure electronic data capture (EDC) system.

The clinical database will reside on a production server hosted by Medidata EDC System. All changes made to the clinical data will be captured in an electronic audit trail and available for review by the sponsor or its representative. The associated Rave software and database have been designed to meet regulatory compliance for deployment as part of a validated system compliant with laws and regulations applicable to the conduct of clinical studies pertaining to the use of electronic records and signatures. Database backups are performed regularly.

The Investigator provides his/her electronic signature on the CRF in compliance with local regulations. Changes to data previously submitted to the sponsor require a new electronic signature by the Investigator acknowledging and approving the changes.

Visual and/or electronic data review will be performed to identify possible data discrepancies. Manual and/or automatic queries will be created in the Medidata EDC system and will be issued to the site for appropriate response. Site staff will be responsible for resolving all queries in the database.

All access to the clinical database will be changed to "Read only" after all data is either "Hard Locked" or "Entry Locked". Once acceptance of the final report or finalization of publications (as applicable) is received, final database storage and archiving activities can begin. Once all of the closeout activities are completed a request to IT is submitted to have the "Database Locked" or Decommissioned and all database access revoked.

In addition, electronic device data from the ICM system will be recorded using the LATITUDE Clarity data management system. This system was designed to be in compliance with federal regulations pertaining to electronic data. The LATITUDE Clarity Data Management System is secured with access limited to appropriately trained personnel and its data resides on Boston Scientific servers which perform regular backups.

